## 8.1. Safety Events

All safety events observed under this protocol are reported through the AdvantageEDC data system throughout the study. Safety events related to vaccine reactogenicity are collected on study-specific forms. Reactogenicity will be collected through the visit on Day 7, if a solicited sign or symptom has started during the seven days post-vaccination and continues it will continue to be reported as a reactogenicity symptom. Only when the reactogenicity event is considered an SAE, as defined below, will it be reported on an AE/SAE form set, in addition to the reactogenicity form. Any symptom starting after seven days post-vaccination will be recorded as an AE. All other

safety events that meet the definition of an AE or SAE that occur throughout the study are reported on the AE/ SAE form set. AE's will be collected through study visit Day 28. SAEs will be assessed through Day 180 and will be reported on the AE/ SAE form set.

## 8.2. Reporting Period

Safety events are reported from the time of the vaccination through completion of the study at 6 months as described above.

#### 8.3. Definitions

#### 8.3.1. Adverse Event (AE)

An adverse event is any untoward medical occurrence in humans, whether or not considered vaccine related, that occurs after the vaccination during the conduct of a clinical trial. Any change from baseline assessment of clinical status, ECGs, routine laboratory tests, X-rays, physical examinations, etc., that is considered clinically significant by the PI is considered an AE.

**Suspected adverse drug reaction** is any AE for which there is a reasonable possibility that the vaccine caused the AE. A reasonable possibility implies that there is evidence to suggest that the study product caused the event.

Adverse reaction is any AE caused by the vaccine.

# 8.3.2. Serious Adverse Events (Defined as Serious Adverse Events, Serious Suspected Adverse Reactions or Serious Adverse Reactions)

An SAE, including a serious suspected adverse reaction or serious adverse reaction as determined by the PI or the Sponsor, is any event that results in any of the following outcomes:

- 1. Death.
- 2. Life-threatening AE (Life-threatening means that the study participant was, in the opinion of the PI or Sponsor, at immediate risk of death from the event as it occurred.)
- 3. Inpatient hospitalization or prolongation of existing hospitalization.
- 4. Persistent or significant incapacity or substantial disruption of the ability to conduct normal life functions.
- 5. Congenital abnormality or birth defect.
- 6. Important medical event that may not result in one of the above outcomes but may jeopardize the health of the study participant or require medical or surgical intervention to prevent one of the outcomes listed in the above definition of serious event.

## 8.3.3. Unexpected Adverse Event

An AE is "unexpected" when its nature (specificity) or severity is not consistent with applicable product information, such as safety information provided in the Investigators' Brochure (IB), the investigational plan or the protocol.

## 8.4. Severity Grading

The study site assigns severity grades to indicate the severity of adverse events and reactions. The severity grading criteria provided in Appendix II grade AEs from Mild (Grade 1) to Life Threatening (Grade 4). All AEs leading to death are Grade 5 events. AEs are graded with the worst severity grade during the illness/symptoms. AE severity will be graded using the attached grading scale (Appendix II) based on the *Division of AIDS (DAIDS) Table for Grading the Severity of Adult and Pediatric Adverse Events*, version 2.0, November 2014, of the US National Institute of Health.

## 8.5. Guidelines for Determining Causality of an Adverse Event

The PI should consider the following question when assessing causality of an AE to study product:

Is there a reasonable possibility that the study product caused the event?

Reasonable possibility implies there is evidence to suggest that the study product caused the reported event. An affirmative answer designates the event as a suspected adverse reaction, and the AE is considered "related". If the answer is no, then the AE is considered "unrelated".

The causality assessment is made on the basis of the available information at the reporting time point. Assessment of causality can change according to follow-up information.

#### 8.6. Assessment of Outcome of Adverse Event

The outcome of adverse event will be assessed as at the time of last observation as per the following categories:

- Recovered/resolved without seguelae
- Recovered/resolved with sequelae
- Ongoing at the end of the study
- Death
- Unknown. The outcome of the AE is not known

#### 8.7. Adverse Event Identification, Resolution and Reporting

To improve the quality and precision of acquired AE data, the PI should observe the following guidelines:

- Whenever possible, use recognized medical terms when recording AEs on the AE CRF. Do not use colloquialisms and/or abbreviations.
- If known, record the diagnosis (i.e., disease or syndrome) rather than component signs, symptoms and laboratory values on the AE CRF (e.g., record congestive heart failure rather than dyspnea, rales, and cyanosis). However, signs and symptoms that are considered unrelated to an encountered syndrome or disease should be recorded as individual AEs on the CRF (e.g., if congestive heart failure and severe headache are observed at the same time, each event should be recorded as an individual AE).

Page **55** of **106** 

AEs occurring secondary to other events (e.g., sequelae) should be identified by the
primary cause. A "primary" AE, if clearly identifiable, generally represents the most
accurate clinical term to record on the AE CRF. If a primary serious AE (SAE) is recorded
on an SAE CRF, events occurring secondary to the primary event should be described in
the narrative description of the case.

For example:

Orthostatic  $\rightarrow$  Fainting and  $\rightarrow$  Head  $\rightarrow$  Neck pain hypotension fall to floor trauma

The primary AE is orthostatic hypotension.

- Grade 2 or higher abnormal laboratory test results will be reported as AEs and assessed
  for severity according to severity grading criteria provided in Appendix II and causality
  (related or unrelated) to the study product. Grade 1 abnormal laboratory test results will
  be entered as AEs if the site PI determines them to be clinically significant.
- Death is an outcome of an event. The event that resulted in the death should be recorded and reported on the SAE CRF.
- For hospitalizations for surgical or diagnostic procedures, the illness leading to the surgical
  or diagnostic procedure should be recorded as the SAE, not the procedure itself. The
  procedure should be captured in the case narrative as part of the action taken in response
  to the illness.
- Pregnancies that occur in study participants are not considered AEs and will be recorded on a separate Pregnancy CRF. Pregnancy outcomes that include stillbirth and any congenital anomalies must be reported as SAEs.

AEs may be discovered through any of these methods.

- Observing the participant.
- Questioning the participant, which should be done in an objective manner.
- Receiving an unsolicited complaint from the participant.
- Review of medical records/source documents.

Each participant will have a scheduled observation following vaccination, including a symptom-directed physical examination, if indicated. They will be monitored in-house for 60 minutes after vaccination. On Days 1 to 7 after vaccination, participants will be instructed to assess and record daily in a participant memory aid any signs and symptoms at the injection site, as well as systemic signs and symptoms. Follow-up visits will be conducted seven days after vaccination, including directed assessment, safety tests and verification of memory aid notes. They will be instructed to call the study team if they observe significant injection site or systemic signs or symptoms, and then to continue monitoring and reporting their condition. All participants will be followed for safety for six months after the vaccination.

#### 8.7.1. **AE** Resolution

All reported AEs should be followed until resolution or stabilization, or until the participant's participation in the study ends. Participants who have an ongoing study product-related SAE at study completion or at discontinuation from the study will be followed by the PI or his designee until the event is resolved or determined to be irreversible, chronic, or stable by the PI.

## 8.7.2. General Recording and Reporting Procedures

A multi-page AE/SAE form set will be used allowing all AEs to be submitted through a single reporting mechanism. SAEs will require additional information reported on additional pages within the Internet data entry system. As appropriate or per request of the Emmes medical monitor or Sponsor medical officer, source documents (e.g., hospitalization discharge summaries) may be uploaded to the AE/SAE form set as well. The PI will treat or refer, as appropriate, participants experiencing AEs and observe them at suitable intervals until their symptoms resolve or their status stabilizes.

#### 8.7.3. SAE Recording and Reporting Procedures

[figure not shown]
SAEs will be recorded on the AE CRF. The site is obligated to report SAEs to the Emmes Coordinating Center within 24 hours of the site's knowledge of the event. The Emmes Coordinating Center will in turn pass on that information to Sponsor and SIIPL.

The following attributes will be assigned by the PI or assignment by designee will undergo documented review by the PI:

- Description
- Date of onset and resolution (if known when reported)
- Severity
- Assessment of relatedness to test article
- Action taken

## 8.7.4. Site Reporting of Events

Figure 3: Reporting Decisions for Adverse Events

- Notify the PI.
- Complete and transmit an AE Form through the Internet data entry system. Information regarding a SAE report must be recorded in the participant's medical chart and entered in the Internet data entry system.
- SAE follow-up reports should include hospital admittance notes, hospital discharge summary, clinical notes, resolution date, treatment, and any other pertinent information regarding the event. If not immediately available, reporting should not be delayed to provide these documents.
- In the event of a death, the SAE Form must be completed and transmitted along with other supporting data (e.g., death certificate, medical notes).

#### 8.8. Serious Adverse Event Notification

#### 8.8.1. Notifications and Review

The PI will provide the Emmes Coordinating Center with data for all SAEs, as defined per the protocol, on a timely manner by entering the information in AdvantageEDC. The Emmes Coordinating Center is responsible for notifying the Sponsor and will do so simultaneously with the reporting to the clinical database. Notification of reported events will be generated at the time of entry into the data system, and all SAEs will be reviewed promptly by the Emmes medical monitor within the data system. As noted above, this notification should be within 24 hours of site awareness of the event. Site personnel will be trained in reporting AEs and SAEs.

The Emmes medical monitor will review all unanticipated events involving risk to participants or others, SAEs and all participant deaths associated with the protocol and will provide a written report. At a minimum, the Emmes medical monitor must comment on the outcomes of the event or problem and, in case of an SAE or death, comment on the relationship to participation in the study. The Emmes medical monitor must also indicate whether he/she concurs with the details of the report provided by the PI.

Summary review of all reported AEs and SAEs will be compiled on a weekly basis to identify any safety trends. Review of safety laboratory tests will also be conducted on a weekly basis.

## 8.8.2. Expedited Reporting

The Emmes Coordinating Center will be responsible for expedited IND Safety Reports and IND Annual reports to the FDA.

When expedited reports as defined below are required, the cover memorandum, MedWatch Form FDA 3500A, and any pertinent attachments will be processed by the Emmes medical monitor and a copy of the completed report will be submitted by fax or courier delivery before the regulatory reporting deadline, to the following persons:

- FDA medical officer as appropriate (submitted as an amendment to the applicable IND)
- PI (who is responsible for forwarding the report to the local/central IRB)
- Safety Review Committee members

If relevant follow-up information becomes available, the Emmes medical monitor will be responsible for obtaining and reviewing details from the site. A follow-up MedWatch form will be completed and forwarded to all parties that received the earlier SAE report. A copy of the safety sections for annual FDA reports will be forwarded to PATH.

Suspected adverse reactions that are serious and unexpected will be reported to the FDA within 15 days, or for deaths and life threatening events that are both suspected adverse reactions and unexpected, within 7 days (per 21 CFR 312.32). The IND Safety Report will be unblinded to treatment allocation and determination of relationship to study product based on the assessment of the sponsor.

Subsequent review by the FDA, the SRC, IRB, or the Sponsor may suspend further study product administration or procedures. The FDA and the study Sponsor with consultation with the SRC retain the authority to suspend additional enrollment for the entire study as applicable.

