#### 2.4.7. Randomization and Vaccination

This is a prospective, randomized, parallel group, double blind clinical study. For arm allocation, a randomization-blocking scheme (1:1:1) will be used. Each block will be of six participants. The vaccine will be supplied to the study site while respecting the randomization block size.

The vaccine will be administered sequentially depending upon the randomization number by unblinded clinical staff not involved with the clinical assessment of study participants. Other investigative site personnel will not be aware of which group the participant has been randomized. The identity of the same cannot be revealed except in an emergency. Study monitor will verify randomization by checking the treatment allocation against the vaccination records at each study visit.

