#### 7. STATISTICAL DESIGN AND ANALYSIS

#### 7.1. Overview and General Design

This study is a Phase 1 double blinded randomized, controlled clinical trial to assess the safety and immunogenicity of the adjuvanted and non-adjuvanted formulation of polyvalent conjugate vaccine composed of serogroups A, C, Y, W, and X *Neisseria meningitidis* capsular polysaccharides (MCV-5). The primary objective is to evaluate the safety of adjuvanted and non-adjuvanted formulations of MCV-5 vaccine. The secondary objective is to assess the immune response of adjuvanted and non-adjuvanted formulations of MCV-5 vaccine.

The primary hypothesis of safety will be fulfilled if no participants develop a vaccine related SAE and the vaccine is well tolerated. The second hypothesis of immunogenicity will be fulfilled if the two formulations of MCV-5 induce immune response as measured by rSBA to all five serogroups of the vaccines.

A detailed statistical analysis plan for preparation of the final study report will be created and made final prior to database lock and unblinding. All statistical analyses will be performed using SAS® software Version 9.3 or later.

Medical history and AEs will be coded using the current version of the Medical Dictionary for Regulatory Activities (MedDRA) dictionary. The frequency count and percentage of participants will be summarized according to the coded terms of system organ class and preferred term. Participant-wise data listing will be provided.

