#### 8.8.4. Notifying the Institutional Review Board

The PI will ensure the timely dissemination of required AE information, including expedited reports, to the IRB in accordance with applicable local regulations and guidelines. The PI is responsible for submitting the IND Safety Report (initial and follow up SAE reports) or other safety information (e.g., revised IB) to the site's IRB and for retaining a copy in the site's study file.

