#### 9.1. Safety Review Committee

A Safety Review Committee, comprised of the PI, a medical expert with experience in vaccine pharmacovigilance not involved with the study, the Emmes medical monitor, SIIPL and PATH medical officer will monitor safety throughout the duration of the study. The Emmes study statistician with assistance of the data management staff will prepare safety reports as needed for SRC discussions. During the vaccination period the SRC will review weekly the safety data. At any time during the study, the Emmes Coordinating Center will notify the SRC of ad hoc review if pause criteria may have been met. The SRC reviews will be summarized with consensus recommendations to the study Sponsor as to whether there are safety concerns and whether the study should continue without change, be modified, or be stopped. The SRC may request review of unblinded safety data by the pharmacovigilance expert in its deliberation. SRC consensus recommendations regarding modifying or stopping further enrolment may involve Sponsor consultation with the local regulatory authority.

The SRC members must be satisfied that the timelines, completeness, and accuracy of the data submitted to them for review are sufficient. Items reviewed by the SRC may include: study participant demographic information; interim/cumulative data for evidence of study-related AEs; data quality, completeness, and timeliness; and factors external to the study, such as scientific or therapeutic developments that may impact participant safety or the ethics of the study. If at any time, a decision is made to discontinue administration of study product in all participants, expeditious notification will be provided by the sponsor to the US FDA and by the PI to the site IRB.

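### Protocol 8.8.2 and 8.8.4 give the blinded PI and the site file an unblinded safety report, and no rule says which relatedness assessment is then analysed

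*Protocol*

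**What the plan says.** **Release of allocation.** Protocol 8.8.2 says of the expedited report: "The IND Safety Report will be unblinded to treatment allocation and determination of relationship to study product based on the assessment of the sponsor". On distribution it says "a copy of the completed report will be submitted by fax or courier delivery before the regulatory reporting deadline, to the following persons". The list names the FDA medical officer, the "PI (who is responsible for forwarding the report to the local/central IRB"), and the SRC members. Follow-up forms go to everyone who received the first report. Under 8.8.4 the PI submits the report to the IRB and is responsible "for retaining a copy in the site's study file". No version with allocation masked is described.

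**Masking.** The Synopsis (Study Design) and 2.4.1 keep the team that assesses safety, and the participants, unaware of allocation. Section 2.4.7 extends this to site personnel other than the unblinded vaccination staff and adds: "The identity of the same cannot be revealed except in an emergency". For the SRC, 9.1 describes one route to unblinded information: "The SRC may request review of unblinded safety data by the pharmacovigilance expert in its deliberation". The PI is a member of that committee.

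**Relatedness.** Protocol 8.5 and 8.7.3 give the relatedness decision to the PI, or to a designee with PI review. Section 8.5 adds: "Assessment of causality can change according to follow-up information". SAP 4.5.1.2 repeats this. Relatedness is part of a primary endpoint (2.4.4), and 7.1 states: "The primary hypothesis of safety will be fulfilled if no participants develop a vaccine related SAE and the vaccine is well tolerated".

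**The concern.** If 8.8.2 and 8.8.4 are followed as written, the PI learns whether the participant with the most consequential kind of event received an MCV-5 formulation or the licensed comparator. The PI also sees the sponsor's view of causality. The PI goes on following the same event and may still change its relatedness. A judgement that feeds a primary endpoint can then be altered with knowledge of treatment. The direction of any bias cannot be predicted: an event after a first-in-human vaccine might be held to a stricter or a more lenient standard than the same event after a vaccine with a large safety database. Because 7.1 makes the hypothesis depend on the absence of a single related SAE, one reclassification is enough to matter.

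**Working it through.** **1. The plan's own figures.** The documents give no figure for expedited reports. Their only design figures rest on 20 recipients per group (Protocol 7.4, SAP 5) and they reproduce:
- Chance of seeing at least one AE with an 11% rate in 20: 1 − 0.89^20 = 0.903 (stated as above 90%).
- One-sided 95% upper bound for 0 of 20: 1 − 0.05^(1/20) = 0.139 (stated as approximately 14%).

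**2. The sections side by side.**

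| Question | Expedited reporting (8.8.2, 8.8.4) | Elsewhere |
|---|---|---|
| Does the PI learn allocation? | Yes, by copy of the completed report | No, except in an emergency (Synopsis, 2.4.1, 2.4.7) |
| Is allocation held at the site outside the pharmacy? | Yes, in the site file | Site personnel blinded (2.4.7) |
| How does the SRC get unblinded information? | Every member receives the report | On request, reviewed by the pharmacovigilance expert (9.1) |

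The first two rows are a direct conflict: an expedited report is a regulatory document, not an emergency disclosure. The third row is a poor fit rather than a contradiction, because 9.1 is worded as a permission.

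**3. Order of events.** Relatedness is judged on what is known when the event is reported (8.5), and SAEs go to the coordinating centre within 24 hours of the site's knowledge (8.7.3). The expedited report follows, within 7 or 15 days, and only because the event is already considered serious, suspected and unexpected. The PI's first assessment therefore normally precedes unblinding. What remains open is any revision after the report arrives. AEs are followed until resolution, stabilization or the end of participation (8.7.1), so there is time for one. Neither document fixes the pre-unblinding assessment as the analysed one. The review before database lock in 10.3 concerns severity, and SAP 6.5 covers relatedness only when it is missing.

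**4. How often this could arise.** With 60 participants and an assumed rate p of serious, suspected and unexpected events, the chance of at least one is 1 − (1 − p)^60:
- p = 0.1%: 1 − 0.999^60 = 5.8%
- p = 0.25%: 1 − 0.9975^60 = 13.9%
- p = 0.5%: 1 − 0.995^60 = 26.0%

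For the 40 MCV-5 recipients alone, to whom the hypothesis refers, the same rates give 3.9%, 9.5% and 18.2%.

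**5. Others in the same block.** Blocks are of six at 1:1:1 (2.4.7), so two per arm. Once one allocation is known, each of the other five has probability 1/5 of the same arm and 2/5 of each other arm, instead of 1/3 each. This identifies nobody.

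**The case against.** The strongest reply is that 8.8.2 is a specific regulatory provision that can be read as an exception to general masking statements, for an event that may never occur in a descriptive Phase 1 trial with no formal testing (7.4). The rarity stands. The exception does not: 2.4.7 allows only an emergency, and nothing in 8.8.2 or 8.8.4 says that the PI's masking is being given up.

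Several stronger readings are tempting, and the documents do not support them.
- *The PI decides relatedness already knowing the arm.* Sections 8.5 and 8.7.3 place the first assessment before the report. The gap concerns later revision, and 8.5 does not say that follow-up information includes allocation.
- *The SRC and emergency-unblinding rules are flatly contradicted.* Section 9.1 is permissive, and the restriction in SAP 4.4.3 governs requests for emergency unblinding, not regulatory reports.
- *The chance of the problem is about 45%.* At the 1.0% SAE rate quoted for Menactra in 13.2, 60 × 0.01 = 0.6 SAEs are expected and 1 − 0.99^60 = 45.3%. That is the chance of an SAE of any cause; expedited cases are a subset.
- *A revision could make an event disappear.* SAEs are counted whatever their relatedness (7.3.1, SAP 9.4.1) and listed individually with relationship and alternate etiology (SAP 9.5). The sponsor's determination also remains in the report.
- *The rest of the block is unmasked.* The shift is small, and under 9.2 a serious adverse reaction automatically pauses vaccination, which limits it further.
- *The IRB and the whole SRC should be kept blind.* Section 8.8.2 allows these bodies, among others, to suspend product administration after reviewing such events. Withholding allocation from them is a real trade-off and is not needed to protect the PI's assessment.

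**Conclusion.** The point holds in a limited form. Protocol 8.8.2 and 8.8.4 conflict with the masking of safety assessors and site personnel, and no rule says which relatedness assessment enters the primary endpoint and the test in 7.1. The result is a route by which a revision made with knowledge of treatment could bias the primary safety conclusion. It is confined to serious, suspected and unexpected events. The range of about 6% to 26% for at least one such event in 60 rests on assumed rates of 0.1% to 0.5%, since the documents give none, and it measures the chance of exposure, not of an actual biased revision. Unblinding the regulator's copy is not at issue. The change is worth making because it is cheap, and because the exposed event is the one that can decide the hypothesis.

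**What to change.** - In 8.8.2 and 8.8.4, provide the PI and the site file with a copy of the report, and of its follow-ups, in which allocation is masked.
- Let the coordinating centre send the unblinded report directly to FDA, to the pharmacovigilance expert, and to the IRB where the IRB requires it.
- Reconcile distribution to the other SRC members with 9.1, without limiting the committee's ability to act on safety. The medical monitor processes these reports (8.8.2) and may answer emergency unblinding requests (SAP 4.4.3), so masking that member's copy would gain nothing.
- State in the protocol and SAP that the PI's causality assessment recorded before any unblinding is the one used for the relatedness endpoints and for 7.1, with any later change listed beside it.
- Leave emergency unblinding unchanged.

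The cost is a few sentences, two versions of a rare report, and an IRB route that does not pass through the PI.
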